### **3-Month Visit (Day 90 ± 30)**

- Collect weight and vital signs
- Confirm concomitant therapy or changes in medication.
- Obtain 3-month CMR scan.
- Blood draw to obtain creatinine levels, hepatic panel, as well as fibrosis/inflammatory biomarkers.
- Review medical history.
- Obtain 1st AFEQT online questionnaire.

- Obtain 1st AFSS online questionnaire.
- Assess for medication compliance.
- Assess for any adverse events.
- Dispense dronedarone or placebo (some/complete 9-month remaining supply) according to randomization assignment.
- Collect unused drug or placebo.
- Troubleshoot/ assess compliance of wearable device.

#### 6-Month and 9-Month Visit/Phone Calls (Day 180 ± 30 and Day 270 ± 30)

- Review medical history and study outcomes.
- Assess for changes in study medication.
- Assess medication compliance.
- Dispense dronedarone or placebo (some/complete remaining supply)
- Provide/Ship patient's ECG monitoring devices.
- Assess compliance/troubleshoot study devices.
- Assess for any adverse events.

#### 12-Month Visit (Day 365 ± 30)

- Collect weight and vital signs.
- Review medical history.
- Blood draw for biomarkers of fibrosis and inflammation.
- Confirm concomitant therapy or changes in medication.
- Obtain 1-year CMR scan.
- Obtain final AFEQT online questionnaire.
- Obtain final AFSS online questionnaire.
- Assess for medication compliance.
- Collect unused drug or placebo.
- Assess for any adverse events.
- Assess compliance/troubleshoot study devices.

#### End of Trial (EOT) Phone Call (Day 395 ± 30)

- Review medical history and study outcomes.
- Assess for changes in study medication.
- Assess medication compliance.
- Assess compliance/troubleshoot for study devices.
- Assess for any adverse events.

## Data Sharing, Data Safety, and Data Integrity Monitoring

All recruited patients will be informed during the initial screening visit of the potential adverse events related to the trial when signing the informed consent form. Adverse event data collection and reporting are required as part of every clinical research trial.

Page 27 of 49

Version 4.0:  
Revision Date: April 27th, 2022

Copyright© April 2022 Tulane University School of Medicine, Academic Research Organization on behalf of the Principal Investigator.  
All rights reserved.

TULANE UNIVERSITY  
Academic Research Organization

### ***Data Sharing Plan***

Tulane University ARO views the sharing of resources with community partners and stakeholders as tantamount to our mission. This concept is at center of what it means to be an “engaged academic institution” – coordinating action and sharing resources to accomplish mutually beneficial objectives within the communities that are our university’s neighbors. We approach our work with colleagues always with this commitment in mind. More precisely, data, models, and software that is not human-subjects sensitive and which is not subject to external copyright restrictions will be made available to the research community at large on a project web site. Human subjects’ sensitive data will only be distributed when it can be done so in a manner that is compliant with all Federal, State, and local regulations, and respects the informed consent agreements with the subjects. Such data will be fully anonymized, and all potentially identifying features will be removed. Full documentation of the data set will be provided. Our findings will be communicated through publications at journals, conferences, and other scientific forums and will be made available on the project web site. As our data will come from multiple sources, and it brings novel combinations of data together, this heightens its potential future utility. We will permit and encourage the reuse of our products by the research community.

We commit to archive our data in accordance with any National Science Foundation (NSF), National Institutes of Health (NIH), and Tulane University ARO guidelines (e.g., de-identification according to IRB and HIPPA regulations) and resources, so future or secondary data collection uses can be steeped from this work. We will also respect the conditions of use of data collected from external sources such as Twitter postings or medical articles. If the University seeks to patent processes developed in the course of this work, it will act in accordance with the NSF Patent Policy.

### ***Data Resource Sharing Plan***

Our data sharing plan will comply with all NIH and Tulane University ARO policies for data sharing. Sharing of data and scientific findings with the research and clinical communities will be executed through publications in peer reviewed journals and presentations at scientific meetings. Data sharing will be implemented in a timely manner. We are very open to sharing EDORA project data with the general scientific community since we believe in the added value of other investigators working on these data.

## **Data Safety and Monitoring**

### ***Data Safety Monitoring Board (DSMB)***

The study will be formally monitored by a Data and Safety Monitoring Board (DSMB). This is an independent board that will have a charter. They will monitor safety data on a regular basis to ensure the continuing safety of the patients involved in this clinical trial. Enrollment will not be paused during these safety reviews.

The DSMB can also recommend modifications to the data management and monitoring procedures in the trial or to the protocol. Every effort will be made to reach a consensus within the DSMB and with the Principal Investigator. In case of disagreement on recommended modifications, the Steering Committee will decide. The DSMB will meet at least two times a year at the discretion of the Chairperson. An emergency meeting may be called at any time throughout the trial should an unforeseen problem arise. The DSMB's full responsibilities, authorities, and procedures will be documented in the DSMB Charter.

#### *Steering Committee (SC)*

The Steering Committee (SC) will act to provide independent oversight of all aspects of the clinical trial. This includes the trials progress, adherence to the protocol and review of any new information regarding the trial's interventions/therapeutic area.

The Steering Committee may meet at any time after the start of the trial, on an ad hoc basis. The steering committee's full responsibilities, authorities, and procedures will be documented in the SC Charter.

#### *Database Lock*

Once the last patient has had their follow-up visit, the database cannot be locked until all data queries have been resolved. Quantitative data will be examined statistically, prior to locking the database. When all such verifications have been completed, the database will become locked, prior to any final data analyses for the EDORA trial.

### **Adverse Events (AEs) and Serious Adverse Events (SAEs)**

An adverse event (AE) is any unforeseen medical occurrence experienced by a patient in the clinical trial. This event can constitute a disease, related signs or symptoms to the investigational drug or study device. All clinical investigators will evaluate and record these events on the appropriate form. Arrhythmias will not require reporting as an AE because the patient will be transmitting ECGs via their ECG device, and these will be reviewed and interpreted by the central monitoring team. A serious adverse event (SAE) is an adverse event that results in death, hospitalization, is life threatening or requires intervention.

For each AE+/SAE, the clinical investigator will record whether an intervention was also required:

- **Intervention-** Surgery or procedure
- **Other treatment-** medication initiation/change, discontinuation
- **None-** no action was taken

In addition, the clinical investigator will also record any clinical outcome of each AE+/SAE:

- Death
- AE resolved or the symptoms/signs that constitute the AE returned to baseline
- AE resolved with permanent sequelae
- Symptoms that constituted the AE are ongoing

Each participating clinical trial site and its investigator has a primary responsibility for the safety of the patients under his or her care. In person visits will occur at 3 and 12-months, and follow-up phone calls/visits will be held at 6, 9-months and towards the end of the clinical trial (Month 13). Clinical investigators or the research team may schedule additional clinic visits according to their standard of

care or as needed to maintain patient safety during the trial. These visits as well as any new or worsening symptoms or events will also be recorded on DACIMA during this time.

All adverse events that occur after randomization will be evaluated throughout the follow-up periods and will be collected and stored on DACIMA.

Serious adverse events (SAE) must be reported in an expedited manner to the IRB and Tulane University ARO, to allow for optimal monitoring of patient safety and care.

Please refer to the Adverse Events & Reporting section for provided timelines on reporting AE, SAE and UP and completing the respective logs.

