A greater volume of new fibrosis ( $\geq 21\%$ ) corresponded with a lower arrhythmia-free survival. In addition to being a significant predictor of AF recurrence, a higher fibrotic burden strongly correlated with a higher risk of stroke (Figure 1), heart failure and mortality in AF patients across multiple studies.

King et al. conducted a 5-year study based on follow-up data from 1,233 patients to quantify LA fibrosis via Late-Gadolinium Enhancement MRI (LGE-MRI).

The study showed atrial fibrosis to be a strong predictor of major cardiovascular and cerebrovascular events. Patients with LA fibrosis stage IV had a 67% increased risk compared to patients with stage I of

the disease. Akoum et al. demonstrated that atrial fibrosis is independently associated with appendage thrombus and spontaneous contrast. Fibrosis is also shown to reduce LA appendage velocity, which is also associated with an increased risk of stroke. In conclusion, progression of fibrosis post-ablation was associated with worse outcomes. For this reason, regarding long-term management of AF, it would be appropriate to look for new therapeutic options that can target a reduction in the progression of fibrosis in order to promote positive outcomes and optimize disease management.

Dronedarone is an anti-arrhythmic drug with properties belonging to Vaughan-Williams class I-IV. It has a similar structure to amiodarone (Class III AAD) and is effective in reducing AF recurrence, AF burden and cardiovascular hospitalization rates in both placebo-controlled trials and in real-world studies. Dronedarone exerts antiarrhythmic effects by inhibiting the outward K1 currents and increasing the refractory period. Additionally, data from multiple prospective observational studies suggest dronedarone may improve QoL. Dronedarone seems to have a reasonable safety profile, with fewer non-cardiovascular risks and a lower risk of ventricular pro-arrhythmia compared to other AADs.

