### *Primary Endpoints*

The primary endpoints of the study are defined as the first occurrence of AA (i.e. atrial fibrillation, atrial flutter, or atrial tachycardia) post-ablation and the progression of atrial fibrosis post-ablation.

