#### **7) Study Participant Safety**

Study participants will be evaluated at multiple timepoints across the study: their in-person 3-month and 12-month visits and their 6, 9 and 13-month phone calls. This evaluation includes any adverse events, especially adverse events (AEs) related to AAD treatment. AEs related to dronedarone are defined in the **Safety/Adverse Event Monitoring Plan** section of this protocol.

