### ***b) Dronedarone***

Antiarrhythmic drugs such as, dronedarone can be prescribed as standard of care. They too carry adverse effects which include; pulmonary events (cough, dyspnea, pulmonary toxicity), thyroid toxicity (hypo- or hyperthyroidism), hepatic toxicity, bradycardia <50bpm, QT-interval prolongation, gastrointestinal events (loss of appetite, nausea, vomiting, abdominal pain and diarrhea), neurological events (dizziness, headache, asthenia, peripheral neuropathy), chest pain or discomfort, heart failure, decompensation in patients with heart failure, and an increase in serum creatinine.

Although a black box warning has been issued by the FDA, dronedarone's associated risk of death and stroke is based on patients with heart failure, decompensated heart failure, or permanent atrial fibrillation. These classes of patients fall into the exclusion criteria and thus, will not be enrolled in this trial. Dronedarone is also contraindicated in AF patients who cannot be cardioverted into normal sinus rhythm.

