### *Adverse Event (AE) Data Collection Procedures*

All AEs, including serious adverse events (SAEs), whether anticipated or unanticipated, will be recorded according to the date of when they first occurred, the severity, and their duration, as well as any treatment that was prescribed.

Any medical condition that was present at the time of randomization, recorded in the patient's baseline medical history which remains unchanged or improves, will not be recorded as an AE at subsequent evaluations. However, worsening of a medical condition that was present at the time of randomization will be considered a new AE and must be reported.

Any abnormal laboratory results at the time of randomization, recorded in the patient's baseline history which remains unchanged will not be recorded as an AE. However, abnormal laboratory results drawn during the trial that are clinically significant will be recorded as an AE and the clinical investigator will assess the severity and relationship it may have to the clinical trial.

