## 4 CONTRAINDICATIONS

MULTAQ is contraindicated in patients with:

- Permanent atrial fibrillation (patients in whom normal sinus rhythm will not or cannot be restored) [*see Boxed Warning, Warnings and Precautions (5.2)*]
- Symptomatic heart failure with recent decompensation requiring hospitalization or NYHA Class IV symptoms [*see Boxed Warning, Warnings and Precautions (5.1)*]
- Second or third-degree atrioventricular (AV) block, or sick sinus syndrome (except when used in conjunction with a functioning pacemaker)
- Bradycardia <50 bpm
- Concomitant use of strong CYP3A inhibitors, such as ketoconazole, itraconazole, voriconazole, cyclosporine, telithromycin, clarithromycin, nefazodone, and ritonavir [*see Drug Interactions (7.2)*]
- Concomitant use of drugs or herbal products that prolong the QT interval and might increase the risk of torsade de pointes, such as phenothiazine antipsychotics, tricyclic antidepressants, certain oral macrolide antibiotics, and Class I and III antiarrhythmics
- Liver or lung toxicity related to the previous use of amiodarone
- QTc Bazett interval  $\geq 500$  ms or PR interval  $>280$  ms
- Severe hepatic impairment
- Pregnancy (Category X): MULTAQ may cause fetal harm when administered to a pregnant woman. MULTAQ is contraindicated in women who are or may become pregnant. If this drug is used during pregnancy, or if the patient becomes pregnant while taking this drug, the patient should be apprised of the potential hazard to a fetus [*see Use in Specific Populations (8.1)*].
- Nursing mothers [*see Use in Specific Populations (8.3)*]
- Hypersensitivity to the active substance or to any of the excipients

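### The adverse-event exemption for arrhythmias is not limited to the atrial endpoint events, so non-atrial arrhythmias can be missing from the safety tables

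*Combined protocol and SAP*

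**What the plan says.** The rule is in the section Adverse Events (AEs) and Serious Adverse Events (SAEs). Directly after telling investigators to evaluate events and enter them on a form, it says: "Arrhythmias will not require reporting as an AE because the patient will be transmitting ECGs via their ECG device". It adds that a central team will interpret the ECGs. It sets no limit by type of rhythm, seriousness or relation to the drug.

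The protocol has a narrower term available, AA. Primary Endpoints uses it for the "first occurrence of AA (i.e. atrial fibrillation, atrial flutter, or atrial tachycardia) post-ablation". The exemption does not use that term.

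Other sections bear on the same events:

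- Study Participant Safety, a secondary endpoint: "This evaluation includes any adverse events, especially adverse events (AEs) related to AAD treatment".
- b) Dronedarone, under the heading for AEs and SAEs related to the trial, lists "bradycardia <50bpm, QT-interval prolongation" among the adverse effects.
- Adverse Event (AE) Data Collection Procedures: "All AEs, including serious adverse events (SAEs), whether anticipated or unanticipated, will be recorded".
- Adverse Events & Reporting requires notification of every SAE within 24 hours and makes no exception for arrhythmias.

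AE records feed two outputs. One is the proportion of patients with AEs, with a 95% confidence interval (Follow-up of SAEs, Unexpected Events, and Related Events). The other is the AE summary that the coordinating centre prepares for DSMB meetings (Unanticipated Problems).

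**The concern.** Keeping efficacy endpoint events off the AE form is a sensible choice, because they are counted elsewhere. The difficulty is that the wording reaches further than the endpoint. A site that sees symptomatic bradycardia in a treated patient finds one section saying that arrhythmias need not be reported as AEs, a second listing bradycardia as an adverse effect of the drug, and a third saying that all AEs are recorded. The documents do not say which governs.

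The study drug is an antiarrhythmic, and AEs related to antiarrhythmic treatment are singled out in the safety endpoint. If sites follow the exemption literally, the safety tables and the DSMB summary can lack a class of events that the protocol itself treats as relevant to the drug.

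**Working it through.** The plan states no figure on this point that could be reproduced. The check is mainly textual, with one piece of arithmetic on the stated reason.

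**Step 1. Is the exemption narrowed anywhere?** The sentence says arrhythmias, without qualification. Neither the AE, SAE and unanticipated-problem sections nor the ECG-monitoring and endpoint sections expressly limit it to AA.

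**Step 2. Does it conflict with other text?** On a literal reading, yes. Bradycardia below 50 bpm is a rhythm disturbance, is listed as an adverse effect under b) Dronedarone, and is not an AA event. The exemption removes it from AE reporting, while Study Participant Safety and the data-collection section call for it. QT prolongation, listed beside it, is an ECG finding and not an arrhythmia, so nothing here rests on it.

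**Step 3. Does the reason given (ECG transmission and central review) support the breadth?**

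*What is counted.* The ECG trial outcome is AA lasting more than 30 seconds (Definition of Trial Outcome using ECG Device), and AF burden is time in AF (Secondary Endpoints). Neither counts a non-atrial rhythm.

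*When the device is worn.* Inputs: five wear periods of 30 days (BodyGuardian section); end-of-trial call at Day 395 ± 30 (Study Schedule) but at Day 365 ± 30 in the Schedule of Events table.

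- Scheduled wear, assuming full adherence: 5 × 30 = 150 days.
- Coverage = 150 / day of the end-of-trial call.
- Nominal Day 395: 150/395 = 38.0%.
- Latest, Day 425 (395 + 30): 150/425 = 35.3%.
- Nominal Day 365 in the table: 150/365 = 41.1%.
- Earliest, Day 335 (365 − 30): 150/335 = 44.8%. This is generous, because it still counts all five windows.

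Scheduled device coverage is thus about 35% to 45% of follow-up. Standard-of-care recordings and voluntary personal-device ECGs may add to it by an amount that the documents do not give.

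*Where findings go.* Device reports are loaded into the trial database, and the vendor may telephone a site about a dangerous rhythm. No step turns a core-lab reading or a vendor call into an AE entry. This gap applies inside the wear windows as well as outside them.

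**Step 4. Is there another route?** The same AE section requires symptoms or events that are new or have worsened to be entered in the trial database. That is mandatory capture, but it does not classify the entry as an AE. CV hospitalization and CV mortality are exploratory endpoints; they do not record the rhythm as an AE, and they miss events managed without admission.

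**Step 5. What follows?** The AE proportions and the DSMB AE summary are built from AEs. An arrhythmia not entered as an AE can be absent from both.

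**The case against.** The strongest case is that this is one loose noun. The protocol often uses arrhythmia for the atrial condition under treatment, and the reason given for the exemption fits the endpoint rhythm. Listing bradycardia under the trial's own AE heading points against a general exemption for it. Reporting may also mean only onward reporting, since Adverse Events & Reporting uses the word for sending AEs to the IRB and the coordinating centre. These readings are open, but none is stated. The sentence follows an instruction to fill in a form and says that arrhythmias need not be reported as AEs, which reads as classification. The ambiguity stands.

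Four stronger readings are tempting, and the documents do not support them.

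- *Serious arrhythmias escape SAE reporting.* A reader might infer this because an SAE is defined as a kind of AE. But the exemption waives reporting as an AE without removing arrhythmias from the AE definition, and the 24-hour rule covers all SAEs without exception. The better reading keeps serious arrhythmias under that rule.
- *Capture is optional or absent.* Database entry of new or worsened events is mandatory. Only the personal-device ECGs are voluntary, and the vendor alert is at the vendor's discretion.
- *The protocol lists ventricular arrhythmia and AV block as adverse effects of dronedarone.* The Background says the drug has "a lower risk of ventricular pro-arrhythmia compared to other AADs", and the product insert gives "Second or third-degree atrioventricular (AV) block, or sick sinus syndrome" as a contraindication. Neither is an adverse-effect listing. Of the rhythm events considered here, only bradycardia is in the protocol's dronedarone list.
- *The dronedarone AE definitions are missing.* Study Participant Safety says "AEs related to dronedarone are defined in the" a monitoring-plan section that the table of contents does not show under that title. The content is apparently what b) Dronedarone supplies, so this is an editorial slip.

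**Conclusion.** The point holds. The exemption is a stated rule, wider than the reason given for it, and if followed literally it can drop non-atrial arrhythmias, including a listed adverse effect of the study drug, from the AE proportions and the DSMB AE summary. It should be corrected.

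Its reach is limited. Secondary endpoints, safety among them, are analysed descriptively, and no primary analysis is affected. What else the DSMB sees depends on a charter that is not in the documents. The number of events missed cannot be stated, because no rate is given. The 38% coverage figure (35% to 45%) assumes full wear and counts only the study device. It tests the stated reason and does not estimate the share of AEs lost. A reader might also infer a biased comparison between arms, since site investigators know the treatment; the documents do not show that recording would differ by arm.

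The conclusion assumes that at least some sites would take the sentence at its word.

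**What to change.** Reconcile the AE definition section, b) Dronedarone, Adverse Events & Reporting and Adverse Event (AE) Data Collection Procedures as follows:

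1. Limit the exemption to non-serious atrial fibrillation, atrial flutter and atrial tachycardia captured as efficacy endpoints.
2. State that any other clinically identified arrhythmia is recorded as an AE by the ordinary route.
3. State that any arrhythmia meeting the SAE definition, atrial ones included, follows the existing SAE rule.
4. Tabulate the events in items 2 and 3 by arm in the DSMB summary and the final safety tables.
5. Correct the section reference in Study Participant Safety while the text is open.

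The cost is a short rewording and modest extra AE form entry at sites. No new assessments, staff or treatment rules are needed. The change covers clinically identified arrhythmias only. Counting events seen solely on core-lab tracings would also need a transfer route to the AE forms, which the protocol does not describe.
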